16.1 Intervention announcement email

16.2 EBPO text

16.3 Participant questionnaire

PRÉCIS

Study Title: Deprescribing to Reduce Injurious Falls among Older Adults with Dementia

Objectives

The overarching objective of this project is to assess the feasibility and acceptability of implementing STOP-FALLS, an evidence-based, deprescribing intervention that targets central nervous system (CNS)-active medications, with older persons with dementia (OPWD) and their care partners, including those from diverse backgrounds. To accomplish this objective, we have the following aims:

Aim 1. Adapt STOP-FALLS for OPWD and their care partner(s). Stakeholder (primary care provider and care partners of OPWD) perspectives will be elicited to inform and guide adaptations. These activities are considered “not human subjects research,” and have been reviewed and determined to be IRB exempt by Kaiser Permanente Washington (KPWA) IRB.

Aim 2. Conduct a one-arm pilot trial of the adapted STOP-FALLS intervention to determine 1) feasibility of reaching OPWD and their care partners, 2) acceptability of the intervention, and 3) whether the intervention was implemented as intended (implementation success).

Aim 3. Establish feasibility of using pragmatic methods to ascertain the following outcomes: 1) medically treated falls (primary outcome), 2) all-cause emergency department visits and hospitalizations (secondary outcome), and 3) nursing home placement (secondary outcome).

Design and Outcomes

The study design for Aims 2 and 3 is a one-arm, health-system embedded pragmatic pilot trial. Outcomes are described above and will be obtained from the virtual data warehouse (VDW) of the health system.

Interventions and Duration

The intervention consists of patient-facing, written brochures on six classes of CNS-active medications and provider decision support in the form of pharmaceutical aids (evidence-based pharmaceutical opinions, or EBPOs). Patient participants will receive a one-time mailing of a brochure, and PCP will receive decision support materials synchronous with the patient participant mailing. Subsequent actions around deprescribing (discussion, tapering) of the medication will be at the discretion of the patient participant and the PCP.

Sample Size and Population

The target sample size is 120 older adults with diagnosed dementia.

STUDY TEAM ROSTER

Principal Investigator:

[name], MS

*University of Washington
Harborview Medical Center
[name]

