1.2. Secondary Objective

To determine the feasibility of using pragmatic methods to ascertain the primary and secondary outcome measures. These outcomes are: 1) medically treated falls (primary outcome), 2) all-cause emergency department visits and hospitalizations, and nursing home placement (secondary outcomes).

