6.2. Description of Evaluations

The pilot study evaluation (Aim 2) will assess 1) feasibility of reaching the target population, 2) acceptability of the intervention, and 3) success of intervention implementation.

Intervention feasibility will be measured by the ability to pull baseline data such as participant contact information, eligibility/ineligibility criteria, and demographics. If no more than 30% of intervention materials are “returned to sender,” we will deem it feasible to reach the target population.

Intervention acceptability will be measured by responses on returned questionnaires. If at least 65% of returned questionnaires indicate the intervention is acceptable and [if applicable] open-ended comments are positive >50% of the time, we will deem the intervention to be acceptable to the target population.

Intervention implementation success will be measured by documentation of a plan to taper in the “sig” field in the participant’s medical record; if at least 35% of participants have a documented taper plan, we will consider the intervention to have been successfully implemented.

Feasibility of obtaining outcomes data from the medical record will be assessed in Aim 3. Outcomes (clinical and utilization) data will be summarized and presented as percent of the study sample with the event (e.g., percent with a medically treated fall; percent with any ED visit or hospitalization, percent with a skilled nursing facility stay). Time to first medically treated fall will also be recorded.

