9.4. Outcomes

9.4.1. Primary outcome

The primary outcome is medically treated falls, defined as falls for which medical care is received. Our measure of the primary outcome will be time to first medically treated fall. The time window of observation for the primary outcome will be 6 months subsequent to the patient-facing materials being distributed to study participants. We will ascertain this outcome from health plan utilization files using International Classification of Disease-10 injury diagnosis and fall-related (V-code or W-code) external cause of injury codes.²⁰⁻²² We will describe fall events according to sex and race/ethnicity.

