9.4.2. Secondary outcomes

Secondary outcomes are 1) all-cause emergency department visits and hospitalizations, and 2) nursing home placement. Secondary outcomes will be ascertained from utilization files of the health plan.

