10.3. Quality Assurance

For Aim 2, to ensure accuracy of the data, we will double input data from the mailed questionnaires. For sig field data, up to 20% of charts will be reviewed to determine if the sig data pulls are accurate.

For Aim 3, the data pulled will be verified as being within the follow-up time window and pertinent to the given study participant by hand-review of the data returned.

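### Aim 3's planned read-outs describe only the events the data pull captured, so they cannot show how complete ascertainment was, and no Aim 3 feasibility criterion is stated

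*Combined protocol and SAP*

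**What the plan says.** The question is about the method of ascertainment. The Précis states Aim 3 as "Establish feasibility of using pragmatic methods to ascertain the following outcomes", and section 1.2 gives the secondary objective as "To determine the feasibility of using pragmatic methods to ascertain the primary and secondary outcome measures". Section 9.1 hypothesizes that the outcomes will prove feasible to assess in this way.

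The planned read-outs are:

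- Section 6.2: "Outcomes (clinical and utilization) data will be summarized and presented as percent of the study sample with the event", followed by "Time to first medically treated fall will also be recorded".
- Section 9.4.1: a description of falls by sex and race/ethnicity.
- Section 10.3, in its Aim 3 paragraph, says that "the data pulled will be verified as being within the follow-up time window and pertinent to the given study participant by hand-review of the data"; this check covers what the pull brings back.

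The source is the same throughout, the health plan's utilization records. Falls are identified "using International Classification of Disease-10 injury diagnosis and fall-related (V-code or W-code) external cause of injury codes". Of the other outcomes, section 9.4.2 says "Secondary outcomes will be ascertained from utilization files of the health plan".

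Section 6.2 sets numeric criteria for the Aim 2 measures: at most 30% returned mail, at least 65% acceptability (with a condition on comments), and at least 35% with a taper plan. It sets none for Aim 3. Section 9.5 extends the green/yellow/red framework to secondary endpoints without naming an Aim 3 measure or cut-off.

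**The concern.** A percentage with the event mixes two things: how often events happened and how many of them the files recorded. The same figure can come from complete capture of a lower event rate or partial capture of a higher one. Time to first fall and the subgroup description are computed from the same captured events. The hand-review can find a record outside the window or attached to the wrong person, but a missed event returns no record to review.

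Observation is a separate gap. Section 6.2 uses the study sample as denominator. The plan does not report how many of the 120 stayed enrolled for the 6-month window, so a participant who left the health plan early would count the same as one observed throughout without an event.

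The pilot is meant to inform a full-scale trial (sections 9.1 and 14). As written, it would hand that trial event percentages with no statement of how complete they are and no rule for judging the method.

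**Working it through.** **1. The plan's own figure.** The only reproducible sample-size figure is n = 78 in section 9.2. It belongs to implementation success (20% versus 35%, one-sided 5% alpha, 90% power), not Aim 3.

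- n = [1.645·√(0.20·0.80) + 1.282·√(0.35·0.65)]² / 0.15² = 71.6.
- With continuity correction: (71.6/4)·[1 + √(1 + 2/(71.6·0.15))]² = 78.1.

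The figure reproduces but does not bear on this point. There is no Aim 3 figure to reproduce.

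**2. What an event percentage identifies.** Observed % = true % × sensitivity + (1 − true %) × (1 − specificity). Assume specificity is 1, so true % = observed % / sensitivity. Assume also an observed 12/120 = 10%; the documents give no rate.

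| Assumed sensitivity | Implied true rate | True events | Missed |
|---|---|---|---|
| 1.0 | 10.0% | 12 | 0 |
| 0.8 | 12.5% | 15 | 3 |
| 0.6 | 16.7% | 20 | 8 |
| 0.5 | 20.0% | 24 | 12 |

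One observed figure fits all four rows, and no planned step would distinguish them.

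**3. What the confidence interval adds.** Fix an assumed true 24/120 = 20% and vary capture (exact 95% intervals):

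- 100% capture: 24/120 = 20%, interval 13.3% to 28.3%.
- 75% capture: 18/120 = 15%, interval 9.1% to 22.7%.
- 50% capture: 12/120 = 10%, interval 5.3% to 16.8%.

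The interval includes 20% at 75% capture and excludes it at 50%. It reflects sampling error only and does not tell the reader which case applies.

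**4. Whether another step fills the gap.**

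- Section 5.1 mentions chart review under Aim 3, but the adjudication it describes (up to 20% of records, 0.20 × 120 = 24) concerns taper flags. It compares yes/no flags with the record, so missed tapers can surface. No such comparison is planned for the Aim 3 outcomes.
- Section 7.3 counts any-cause hospitalization as an SAE, and section 7.3.1 allows record review for SAEs. No comparison with the automated pull is planned.
- If the 20%/35% bands in section 9.5 were applied to event percentages, fewer than 24 of 120 with an event would read as red and 42 or more as green (0.20 × 120 = 24; 0.35 × 120 = 42). That grades how common events are and says nothing about ascertainment.

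**The case against.** The strongest reply is that feasibility is not validity. Sections 5.1 and 6.1 describe Aim 3 as obtaining outcome data: adapt existing STOP-FALLS code, run the pull, build a dataset, summarize. Event percentages show that this pipeline runs, and measuring sensitivity is a different question. This stands in part: a formal validation study is not required of a pilot this size. But section 1.2 speaks of ascertaining the outcomes, and showing that a percentage can be computed is a thin answer. Reuse of the code does not settle it, since section 2.2 says STOP-FALLS excludes dementia and the documents report no capture figure.

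Four stronger readings are tempting, and the documents do not support them.

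- *The plan will call ascertainment feasible whatever the data show.* It states no rule for calling it feasible or infeasible. The pull could also fail, or the hand-review could find errors.
- *The full-scale trial will be planned on a wrong event rate.* No section says the pilot percentage will be the planning rate. If that trial uses the same coded outcome, the captured rate may be the relevant one.
- *A treated fall without an external-cause code is scored as no fall.* Section 9.4.1 joins the two code types with *and*, so this reading is likely. But Table 2 lists them separately, and no section says both must be present on an encounter.
- *Nothing but event percentages is planned.* Time to first fall, falls by subgroup and the hand-review are also planned, though none looks beyond captured events.

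**Conclusion.** The point holds as a mismatch between objective and measure. Aim 3 asks about ascertainment, the planned summaries and checks describe only captured events, and no Aim 3 criterion is given. It is a worthwhile, inexpensive improvement to a descriptive one-arm pilot; there is no arithmetic error.

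The amount of under-capture is unknown and may be small. The twofold range in the working (10% to 20% true for 10% observed) rests on assumed event rates, assumed sensitivities and perfect specificity, and illustrates only that the percentage cannot identify capture. The external-cause argument applies to falls alone; the enrollment argument applies to all three outcomes.

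**What to change.** In sections 6.2 and 9.5, add Aim 3 feasibility measures from data the study already accesses:

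- **(a) Coding completeness for falls.** Among follow-up encounters with an injury diagnosis, report the percent carrying any external-cause code. Report the fall percentage with and without injury encounters that lack one. The larger figure is a bound, since some of those encounters are not falls. Table 2 already lists injury and fall-related codes.
- **(b) Completeness of observation.** Report the percent of the 120 continuously enrolled, or followed to death, through month 6. Report event percentages also among those fully observed. Enrollment start and stop dates are in Table 1 for identifying participants; the pull must extend to the follow-up window.
- **(c) Criterion.** State in advance the level of (a) and (b) below which ascertainment would not be called feasible. The level is the sponsor's choice. State also that the 20%/35% bands do not apply to event percentages.

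The cost is two extra tabulations, a short extension of the enrollment pull and some wording. The limitation is that (a) measures coding completeness for falls only and (b) measures observation, so neither gives sensitivity for ED visits, hospitalizations or nursing home entry.

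Chart-based agreement in the taper-review sample is optional. It goes beyond the sig-field review in section 10.2, and with at most 24 charts it would be imprecise. At an assumed 20% fall rate about 5 charts would contain a fall (24 × 0.20 = 4.8), and even 0 of 24 charts with a missed event leaves an exact 95% upper limit of 14.2%.

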7. SAFETY ASSESSMENTS

7.1. Specifications of Safety Parameters

Comprehensive medication management is part of the KPWA standard of care, and any medication changes will be made by the participant and their PCP. This is consistent with usual care. There is no requirement for participants, care partners or PCPs to engage in discussion about medication safety or deprescribing. The intervention is education and designed to offer participants and their care partners information to understand the risks of CNS-active medications for older adults with dementia. The intervention does not alter a participant's medication prescriptions.

There is still the possibility for adverse effects from the intervention. These are described under 7.3., below.

7.2. Methods and Timing for Assessing, Recording and Analyzing Safety Parameters

This research involves testing an educational intervention, and therefore the main risk is breach of confidentiality. For more detail on the steps we will take to ensure patient confidentiality, see section 11.3.

To allow for the possibility that adverse events may result from the intervention, we define adverse events and reporting procedures in the following section.

Throughout the study period, any clinic champion or PCP will be able to report safety concerns via the study's project manager's voicemail.

7.3. Adverse Events (AE) and Serious Adverse Events (SAE)

AEs for this study include:

- Medication withdrawal symptoms (e.g., for opioids – nausea, vomiting, diarrhea)

- Worsening of underlying condition for which medication was prescribed (e.g., for antipsychotics – behavioral and psychological symptoms of dementia (BPSD) (e.g., agitation, aggression, psychosis)

The severity of AE is likely to be moderate and would be *expected* as a result of reduction in medications especially if the medication were withdrawn rapidly or abruptly.

SAEs for this study include:

- Emergency department visit or hospitalization for management of medication withdrawal symptoms
- Emergency department visit or hospitalization for management of BPSD or re-emergence of other symptoms for which the medication was prescribed
- Hospitalization due to any cause
- Death due to any cause

The above events would be *expected* given the nature of the intervention and the population under study (i.e., older adults with dementia).

7.3.1. Reporting Procedures

Contact information (telephone / voicemail) for the study’s project manager will be provided to intervention clinics, and clinic champions and PCPs will be invited to report any possible adverse events resulting from the trial. For each report, the site PI and study PI will review the potential concern. Review of the electronic medical record for adverse events will be restricted to SAE.

Adverse events that are serious and unexpected will be reported to the IMPACT Collaboratory Regulatory and Data Team Leader, the NIA IMPACT Collaboratory Program Officer, and the project’s Safety Officer and, if related to the intervention, to the Advarra IRB, within 48 hours of the study team’s knowledge of the event.

All deaths will be reported to the IMPACT Collaboratory Regulatory and Data Team Leader, the NIA IMPACT Collaboratory Program Officer, and the project’s Safety Officer within 24 hours of the study team’s knowledge of death.

All unanticipated problems (UPs) will be reported to the IMPACT Collaboratory Regulatory and Data Team Leader, Advarra IRB, NIA IMPACT Collaboratory Program Officer, and the project’s Safety Officer within 48 hours of the study’s knowledge of the problem.

The summaries of all previously reported unexpected and related SAEs, deaths, and UPs, *as well as* all other SAEs and AEs will be reported to IMPACT Collaboratory Regulatory and Data Team Lead, Advarra IRB, NIA IMPACT Collaboratory PO, and the project's Safety Officer at a minimum every 6 months, or at a frequency requested by the IMPACT Collaboratory.

7.3.2. Follow-up for Adverse Events

Adverse events will be reviewed by the Safety Officer for the study as described above, who will determine the need for any follow-up actions and define the exact nature of those actions.

7.4. Safety Monitoring

An independent Safety Officer has been appointed by the NIA IMPACT Collaboratory to serve as the data safety monitor.

8. INTERVENTION DISCONTINUATION

For this pilot study of a one-time, pragmatic, educational intervention, we do not have intervention discontinuation criteria.

9. STATISTICAL CONSIDERATIONS

9.1. General Design Issues

This is a one-arm pilot study to inform a future full-scale, stage 4 embedded pragmatic clinical trial (ePCT). The one-arm design is justified because the primary objective is to establish feasibility and acceptability of the intervention. We hypothesize that the intervention will be feasible to implement, acceptable to patients and clinicians, and that outcomes will be feasible to assess via pragmatic methods.

9.2. Sample Size and Randomization

For Aims 2 and 3, our sample size calculations are based on the framework of “green”, “yellow” and “red” lighting for pilot feasibility trials.³⁹ Based on our primary endpoint, which is implementation success,¹⁷ assuming the upper boundary of the “red” zone is 20% and the lower boundary of the “green” zone is 35%, the sample size required for analysis given 90% power and one-sided 5% alpha is $n=78$ (intervention arm only). Specifically, if the true rate is in the “green” zone with a sample size of 78, we have 90% power for the study to not be defined as “red” lighted. We will increase the sample size to 120 to be able to have 90% power across all secondary endpoints as well.

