9.5. Data Analyses

We will summarize measures of feasibility and acceptability using binary outcomes and calculating proportions and 95% confidence intervals using simple descriptive analysis. For our primary endpoint of implementation success, following the framework proposed for pragmatic pilot trials,³⁹ if 35% have a documented taper plan, the trial will be “green” lighted to move forward to a confirmatory study; if 20%–<35% have a documented taper plan, it will be “yellow” lighted, meaning that the intervention needs to be modified if to move forward; and if <20% have a documented taper plan, it will be “red” lighted, meaning that the intervention is a “no go”. The same framework will be applied across secondary endpoints. We will examine differences by relevant sociodemographic characteristics (e.g., race, ethnicity, sex) for each outcome using the same criteria.

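### As written, the 20%/35% decision bands in section 9.5 do not carry the one-sided 5% alpha on which section 9.2 sizes the trial: at n=120 a true rate of 18% escapes red 31.9% of the time

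*Combined protocol and SAP*

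**What the plan says.** Section 9.2 names implementation success (a documented taper plan) as the primary endpoint, with 20% as the top of the red zone and 35% as the bottom of the green zone. It gives 78 as "the sample size required for analysis given 90% power and one-sided 5% alpha" and explains the power in terms of the traffic-light decision: with a true rate in the green zone, "we have 90% power for the study to not be defined as “red” lighted". The sample is then raised to 120 for the sake of the secondary endpoints.

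Section 9.5 sets the decision rule, "following the framework proposed for pragmatic pilot trials" (reference 39, also cited in 9.2). An observed 35% is green. From 20% to below 35% is yellow, "meaning that the intervention needs to be modified if to move forward". For the lowest band, "if <20% have a documented taper plan, it will be “red” lighted", which the section equates with a no-go. Otherwise 9.5 specifies only proportions with 95% confidence intervals. It mentions no hypothesis test, critical count or alpha. It adds: "The same framework will be applied across secondary endpoints". Section 6.2 also compares the observed percentage with 35%.

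**The concern.** The two sections describe different rules for one decision. A one-sided 5% test of 20% requires an observed proportion well above 20% before red is ruled out. The bands in 9.5 rule out red as soon as the observed proportion reaches 20%. Someone reading 9.2 would expect a chance of about 5% of leaving red when the true rate is at the top of the red zone. Under 9.5 that chance is roughly one half.

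Red stops the programme and yellow lets it continue after modification, so the stated error rate bears on whether a weak intervention is carried forward. If a test was intended, the sections also conflict on the outcome for some results: two analysts could report no-go and modify from the same data.

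**Working it through.** **Inputs.** From 9.2: p0 = 0.20, p1 = 0.35, one-sided alpha 0.05, power 0.90, n = 78, planned n = 120. From 9.5: red below 20%, yellow 20% to below 35%, green at 35% (read as 35% or more).

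**1. Reproducing n=78.** One-sample normal approximation:

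n = [(1.645·√(0.20·0.80) + 1.282·√(0.35·0.65)) / 0.15]² = 71.6

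With the continuity correction:

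(71.6/4)·[1 + √(1 + 2/(71.6·0.15))]² = 78.1

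So 78 is the size of a continuity-corrected 5% test. In exact binomial terms n=78 narrowly misses one target or the other: a cut of 22 gives alpha 5.2% and power 91.8%; a cut of 23 gives 2.9% and 87.4%.

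**2. The 9.5 bands as counts.** At n=120, 0.20 × 120 = 24 and 0.35 × 120 = 42, so not red means 24 or more and green means 42 or more. At n=78, 0.20 × 78 = 15.6, so not red means 16 or more.

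**3. Chance of not being red under the bands,** P(X ≥ cut) with X binomial(n, p):

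| True rate | n=120 (≥24) | n=78 (≥16) |
|---|---|---|
| 12% | 0.8% | 2.2% |
| 15% | 8.3% | 11.7% |
| 18% | 31.9% | 32.4% |
| 19% | 42.6% | 41.1% |
| 20% (boundary) | 53.6% | 50.0% |
| 35% | 99.99% | 99.8% |

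At n=120 the probability reaches 5% at a true rate of about 14.2%, so it exceeds 5% from there up to 20%.

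**4. The green cut at n=120.** P(X ≥ 42) is about 0.009% at a true 20% and 53.4% at a true 35%. The 5% does not describe this cut either.

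**5. Could the bands have produced n=78?** With the cut at 20% of n, rounded up, P(not red | 35%) is 89.7% at n=17 and 92.2% at n=18, and stays at or above 90% for every n from 18 to 199 (the range checked). The 90% requirement would have been met with far fewer than 78, so n=78 comes from the 5% test.

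**6. What a 5% test would need at n=120.** P(X ≥ 31 | 0.20) = 7.2% and P(X ≥ 32 | 0.20) = 4.7%, so the cut is 32 (32/120 = 26.7%).

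| True rate | Not red, bands (≥24) | Not red, 5% test (≥32) |
|---|---|---|
| 18% | 31.9% | 1.2% |
| 20% | 53.6% | 4.7% |
| 25% | 91.7% | 37.0% |
| 30% | 99.5% | 81.4% |
| 35% | 99.99% | 98.0% |

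The rules disagree for 24 to 31 of 120 (20.0% to 25.8%): yellow under the bands, red under the test.

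**The case against.** The best defence is that both sections cite the same framework and the title of reference 39 mentions a hypothesis test, so a test may be implied. The source cannot be consulted here. But 9.5 writes out complete bands and imports no cut-off, so an analyst would apply the bands. If a test was meant, the case for correcting the text is stronger, because the bands then give the wrong light for 24 to 31 of 120.

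Second, 9.2 never says in words that alpha is the chance of leaving red; it puts only the power in words, and that is exceeded. This is true, but a one-sided alpha for a test whose null is the top of the red zone has no other natural meaning.

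Third, 9.5 classes 20% itself as yellow, so 53.6% is a limiting value and not a misclassification rate; any cut applied to an observed proportion gives about one half at its own threshold. This stands, and it is why 18% is the better illustration. Even if exactly 24 of 120 counted as red, the figure at 18% would be 24.1%.

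Fourth, this is a one-arm pilot, and escaping red leads to yellow, not to an unmodified go. This also stands and limits the seriousness of the point.

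**Conclusion.** The concern holds. Neither error rate in 9.2 describes the rule in 9.5, at n=78 or at n=120. The power difference is harmless, since 90% is exceeded. The alpha difference is not: the chance of escaping red is 31.9% at a true 18% and above 5% for true rates from about 14.2% to 20%. The sample size need not change, and the consequence is confined to red versus yellow. It should be fixed because 9.2 attaches an error rate to the no-go decision on the primary endpoint that the written rule does not have.

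The figures assume that 9.5 is complete as written, that 120 participants are analysed (section 5.1 says up to 120), and that participants are independent. The last is an approximation, because section 5.1 allows up to four clinics and tapering is decided with the patients' PCPs.

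**What to change.** Keep the 9.5 bands. In 9.2, say that the 5% alpha and 90% power are the basis for n=78 and are not properties of the bands. Report the bands' operating characteristics at n=120: not red 54% at a true 20%, 32% at 18%, 8% at 15% and 99.99% at 35%; green 53% at 35%. State the independence assumption and recompute if fewer than 120 are analysed. In 9.5, say whether the secondary endpoints are also judged on observed bands.

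This costs two or three sentences, with no change to recruitment, data, n or the decision rule. The price is that the plan no longer claims 5% error control for leaving red.

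If the sponsor did intend a 5% test, 9.5 should instead state the critical count before taper-plan data are seen: at n=120, not red at 32 or more (exact alpha 4.7%, power 98.0% at 35%), recomputed at the n analysed. That is a change of decision rule with a real cost: results of 24 to 31 of 120 move from yellow to red, and the chance of not being red falls from 91.7% to 37.0% at a true 25% and from 99.5% to 81.4% at a true 30%. The choice is the sponsor's; either way the two sections should describe one rule.
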